9.1.2 Reporting of Pregnancy and Lactation to the Sponsor

Although pregnancy and lactation are not considered adverse events, it is the responsibility of Investigators or their designees to report any pregnancy or lactation in a subject (spontaneously reported to them), that occurs during the trial.

Pregnancies and lactations that occur after the consent form is signed, but before treatment allocation/randomization, must be reported by the Investigator if they cause the subject to be excluded from the trial, or are the result of a protocol-specified intervention, including, but not limited to, washout or discontinuation of usual therapy, diet, placebo treatment or a procedure.

Pregnancies and lactations that occur from the time of treatment allocation/randomization through 120 days, or 30 days following cessation of treatment if the subject initiates new anti-cancer therapy, whichever is earlier, must be reported by the Investigator. All subjects and female partners of male subjects who become pregnant must be followed to the completion/termination of the pregnancy. Pregnancy outcomes of spontaneous abortion, missed abortion, benign hydatidiform mole, blighted ovum, fetal death, intrauterine death, miscarriage and stillbirth must be reported as serious events (Important Medical Events). If the pregnancy continues to term, the outcome (health of infant) must also be reported.

Such events must be reported within 24 hours to the Sponsor and within 2 working days to the product's manufacturer safety division.

9.1.3 Immediate Reporting of Adverse Events to the Sponsor

9.1.3.1 Serious Adverse Events

A serious adverse event is any adverse event occurring while the subject is enrolled into the study that:

- Results in death;
- Is life threatening;
- Results in persistent or significant disability/incapacity;
- Results in or prolongs an existing inpatient hospitalization;
- Is a congenital anomaly/birth defect;
- Is another important medical event

Note: In addition to the above criteria, adverse events meeting either of the below criteria, although not serious per ICH definition, are reportable to the Merck in the same timeframe as SAEs to meet certain local requirements. Therefore, these events are considered serious by Merck for collection purposes.

- Is a new cancer (that is not a condition of the study);
- Is associated with an overdose.

Product: MK-3475

Protocol/Amendment No.: Amendment 5, 21 October 2019

Refer to Table 8 for additional details regarding each of the above criteria.

Progression of the cancer under study is not considered an adverse event unless it results in hospitalization or death.

For the time period beginning when the consent form is signed until treatment allocation/randomization, any serious adverse event, or follow up to a serious adverse event, including death due to any cause other than progression of the cancer under study, that occurs to any subject must be reported within 24 hours to the Sponsor and within 2 working days to Merck Global Safety if it causes the subject to be excluded from the trial, or is the result of a protocol-specified intervention, including, but not limited to, washout or discontinuation of usual therapy, diet, placebo treatment or a procedure.

For the time period beginning at treatment allocation/randomization through 90 days following cessation of treatment, or 30 days following cessation of treatment if the subject initiates new anticancer therapy, whichever is earlier, any serious adverse event, or follow up to a serious adverse event, including death due to any cause other than progression of the cancer under study, whether or not related to the investigational product, must be reported within 24 hours to the Sponsor (and Merck Global Safety if a Merck product.)

Additionally, any serious adverse event, considered by a qualified physician to be related to the investigational product that is brought to the attention of the Investigator at any time also must be reported immediately to the Sponsor and to product's manufacturer.

SAE reports and any other relevant safety information are to be forwarded to the FDA and the drug manufacturer's safety division, as appropriate (Merck Global Safety [contact]).

A copy of all 15 Day Reports and Annual Progress Reports are to be submitted as required by FDA, or other local regulators. Investigators will cross reference this submission according to local regulations to the Merck Investigational Compound Number (IND, CSA, etc.) at the time of submission. Additionally Investigators will submit a copy of these reports to Merck & Co., Inc. (Attn: Worldwide Product Safety; [contact]) at the time of submission to FDA.

9.1.3.2 Events of Clinical Interest

Selected non-serious and serious adverse events are also known as Events of Clinical Interest (ECI) and must be reported within 24 hours to the Sponsor and within 2 working days to the product manufacturer safety division.

For the time period beginning when the consent form is signed until treatment allocation/randomization, any ECI, or follow up to an ECI, that occurs to any subject must be reported within 24 hours to the Sponsor and within 2 working days to Merck Global Safety if it causes the subject to be excluded from the trial, or is the result of a protocol-specified

Product: MK-3475

Protocol/Amendment No.: Amendment 5, 21 October 2019

intervention, including, but not limited to, washout or discontinuation of usual therapy, diet, placebo treatment or a procedure.

For the time period beginning at treatment allocation/randomization through 90 days following cessation of treatment, or 30 days following cessation of treatment if the subject initiates new anticancer therapy, whichever is earlier, any ECI, or follow up to an ECI, whether or not related to Merck product, must be reported within 24 hours to the Sponsor and within 24 hours to Merck Global Safety.

Events of clinical interest for this trial include:

1. An overdose of study drug, as defined in Section 9.1.1 - Definition of an Overdose for this Protocol and Reporting of Overdose to the Sponsor, that is not associated with clinical symptoms or abnormal laboratory results.
2. An elevated AST or ALT laboratory value that is greater than or equal to 3X the upper limit of normal and an elevated total bilirubin laboratory value that is greater than or equal to 2X the upper limit of normal and, at the same time, an alkaline phosphatase laboratory value that is less than 2X the upper limit of normal, as determined by way of protocol-specified laboratory testing or unscheduled laboratory testing.*

***Note:** These criteria are based upon available regulatory guidance documents. The purpose of the criteria is to specify a threshold of abnormal hepatic tests that may require an additional evaluation for an underlying etiology.

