5.2.3.3 Dose Modification (Escalation/Titration/Other)

Adverse events (both non-serious and serious) associated with pembrolizumab exposure may represent an immunologic etiology. These adverse events may occur shortly after the first dose or several months after the last dose of treatment. Pembrolizumab must be withheld for drug-related toxicities and severe or life-threatening AEs as per Table 3 below. See Section 5.4.1 for supportive care guidelines, including use of corticosteroids.

Table 3

Dose Modification Guidelines for Drug-Related Adverse Events

Toxicity	Hold Treatment For Grade	Timing for Restarting Treatment	Treatment Discontinuation
Diarrhea/Colitis	2-3	Toxicity resolves to Grade 0-1	Toxicity does not resolve within 12 weeks of last dose or inability to reduce corticosteroid to 10 mg or less of prednisone or equivalent per day within 12 weeks
	4	Permanently discontinue	Permanently discontinue
AST, ALT, or Increased Bilirubin	2	Toxicity resolves to Grade 0-1	Toxicity does not resolve within 12 weeks of last dose
	3-4	Permanently discontinue (see exception below) ^a	Permanently discontinue
Type 1 diabetes mellitus (if new onset) or Hyperglycemia	T1DM or 3-4	Hold pembrolizumab for new onset Type 1 diabetes mellitus or Grade 3-4 hyperglycemia associated with evidence of beta cell failure	Resume pembrolizumab when patients are clinically and metabolically stable
Hypophysitis	2-4	Toxicity resolves to Grade 0-1. Therapy with pembrolizumab can be continued while endocrine replacement therapy is instituted	Toxicity does not resolve within 12 weeks of last dose or inability to reduce corticosteroid to 10 mg or less of prednisone or equivalent per day within 12 weeks
Hyperthyroidism	3	Toxicity resolves to Grade 0-1	Toxicity does not resolve within 12 weeks of last dose or inability to reduce corticosteroid to 10 mg or less of prednisone or equivalent per day within 12 weeks
	4	Permanently discontinue	Permanently discontinue
Hypothyroidism		Therapy with pembrolizumab can be continued while thyroid replacement therapy is instituted	Therapy with pembrolizumab can be continued while thyroid replacement therapy is instituted
Infusion Reaction	2 ^b	Toxicity resolves to Grade 0-1	Permanently discontinue if toxicity develops despite adequate premedication
	3-4	Permanently discontinue	Permanently discontinue

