5.3.1 Acceptable Concomitant Medications

All treatments that the Investigator considers necessary for a subject's welfare may be administered at the discretion of the Investigator in keeping with the community standards of medical care. All concomitant medication will be recorded on the case report form (CRF), including all prescription, over-the-counter (OTC), herbal supplements, and IV medications and fluids. If changes occur during the trial period, documentation of drug, dosage, frequency, route, and date should also be included on the CRF.

All concomitant medications received within 28 days before the first dose of trial treatment and 30 days after the last dose of trial treatment should be recorded. Concomitant medications administered after 30 days after the last dose of trial treatment should be recorded for SAEs and ECIs as defined in Section 9.0.

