5.3.2 Prohibited Concomitant Medications

Subjects are prohibited from receiving the following therapies during the Screening and Treatment Phase (including retreatment for post-complete response relapse) of this trial:

- Anti-cancer systemic chemotherapy or biological therapy
- Immunotherapy not specified in this protocol
- Chemotherapy not specified in this protocol
- Investigational agents other than MK-3475
- Radiation therapy
- Live vaccines within 30 days prior to the first dose of trial treatment and while participating in the trial. Examples of live vaccines include, but are not limited to, the following: measles, mumps, rubella, chicken pox, yellow fever, rabies, BCG (with the exclusion of BCG for treatment), and typhoid (oral) vaccine. Seasonal influenza vaccines for injection are generally killed virus vaccines and are allowed; however, intranasal influenza vaccines (e.g. Flu-Mist[®]) are live attenuated vaccines and are not allowed.
- Glucocorticoids for any purpose other than to modulate symptoms from an event of clinical interest of suspected immunologic etiology. The use of steroids for treatment of a grade 1 or 2 immune mediated adverse event may delay BCG treatment for up to 2 weeks with the expectation that steroid treatment will be discontinued prior to the next BCG treatment cycle. A delay of longer than 2 weeks will permanently discontinue the

patient from BCG treatment within the study or permanent withdrawal of the patient from the study. The choice will be at the discretion of the treating Investigator. Steroid treatment for grade 3 or higher immune mediated events will require discontinuation of BCG treatment and/or withdrawal from the study.

- The use of physiologic doses of corticosteroids may be approved after consultation with the Sponsor.
- Drug combinations containing immunosuppressants and/or bone marrow depressants and/or radiation. The above mentioned therapies interfere with the development of the immune response and should not be used in combination with BCG.
- Antimicrobial therapy may interfere with the effectiveness of BCG treatment. If antimicrobial therapy is required, BCG treatment should be delayed as appropriate.

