Subjects who, in the assessment by the Investigator, require the use of any of the aforementioned treatments for clinical management should be removed from the trial treatment or delayed in the case of antimicrobial treatment. Subjects may receive other medications that the Investigator deems to be medically necessary.

The Exclusion Criteria describes other medications which are prohibited in this trial.

There are no prohibited therapies during the Post-Treatment Follow-up Phase.

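### General AE collection stops at 30 days and the ECI list names no immune event beyond a liver-test pattern, so new non-serious immune toxicity on days 31–90 is not clearly required to be collected

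*Combined protocol and SAP*

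**What the plan says.** **The ECI term.** Section 5.3.2 prohibits "Glucocorticoids for any purpose other than to modulate symptoms from an event of clinical interest of suspected immunologic etiology". This presumes that immune-mediated events are ECIs. Section 9.1.3.2 has the only ECI list, introduced by "Events of clinical interest for this trial include". It has two items: an overdose "that is not associated with clinical symptoms or abnormal laboratory results", and AST or ALT at least 3 times the upper limit of normal with total bilirubin at least 2 times and alkaline phosphatase below 2 times.

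**The windows.** Sections 7.1 (footnote j), 8.1.2.2 and 9.0 all end general AE collection 30 days after the last treatment. Sections 9.1.3.1 and 9.1.3.2 carry SAEs and ECIs to 90 days, or to 30 days if new anticancer therapy starts. Related SAEs that reach the investigator are reportable at any time.

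**Medication.** Section 5.3.1 says: "Concomitant medications administered after 30 days after the last dose of trial treatment should be recorded for SAEs and ECIs as defined in Section 9.0".

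**Late onset.** On immune-type events, Section 5.2.3.3 says: "These adverse events may occur shortly after the first dose or several months after the last dose of treatment".

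**Analysis.** Section 10.1 answers the primary safety objective with the proportion of patients having each AE, by CTCAE grade.

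**The concern.** The 90-day ECI window is the one mechanism in the protocol that could extend collection of non-serious events past day 30. Section 5.3.2 reads as if immune events were inside it, but the list leaves out colitis, pneumonitis, hypophysitis, thyroid disorders, new-onset diabetes and nephritis, all of which appear in Table 3 and Section 5.4.1. The primary analysis is a simple proportion, and an event that was never collected cannot enter it. What is at stake is the completeness of the late immune-toxicity count in a 15-subject safety study.

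The second problem is the term itself. Read literally, the steroid exception is nearly empty: the first ECI has no symptoms to treat, and the second is a laboratory threshold. A site that reads it that way could then reach the sentence saying that subjects who "require the use of any of the aforementioned treatments for clinical management should be removed from the trial treatment".

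**Working it through.** There is no statistical figure in the plan to reproduce here. The check is a calendar and a cross-reading of definitions.

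**Calendar** (study day = 7 × (week − 1) + 1, from the visit weeks in the Section 7.1 flow chart):
- Last MK-3475 dose, Week 16: 7 × 15 + 1 = day 106.
- General AE collection ends: 106 + 30 = day 136.
- SAE and ECI collection ends: 106 + 90 = day 196, if no new anticancer therapy starts.
- Interval covered only by the SAE and ECI rules: 196 − 136 = 60 days.
- Week 19 cystoscopy: 7 × 18 + 1 = day 127. The 3-month visit, taken as 91 days later, is about day 218, or 218 − 106 = 112 days after the last dose.

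The safety visit comes about 30 days after the last dose and the next scheduled contact at about day 112. No scheduled visit falls on days 31–90.

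**How a new immune event starting on days 31–90 is classified:**

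| Rule | Captured? |
|---|---|
| General AE (7.1 footnote j, 8.1.2.2, 9.0) | No; the window has closed |
| SAE (9.1.3.1) | Only if a seriousness criterion is met |
| ECI (9.1.3.2) | Only if it meets the liver pattern |
| Follow-up of open AEs (8.1.6.5) | No; this applies to events above Grade 1 already present |
| Concomitant medication (5.3.1) | Only if the event is an SAE or ECI |

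A new, non-serious event outside the liver pattern fails every row. Section 8.1.6.6 does not list AEs among the items to gather in follow-up.

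**Weight of one missed subject:** 1 / 15 = 6.7 percentage points on the proportion for that AE.

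**The steroid wording, read in full.** After the exception, the same bullet in Section 5.3.2 continues: "The use of steroids for treatment of a grade 1 or 2 immune mediated adverse event may delay BCG treatment for up to 2 weeks". It then adds: "Steroid treatment for grade 3 or higher immune mediated events will require discontinuation of BCG treatment and/or withdrawal from the study". Section 5.2.1.1.3 repeats both provisions, Table 3 uses the ability to reduce corticosteroids as a criterion, and Section 5.4.1 directs corticosteroids for most of the immune events it covers. The text as a whole therefore expects steroids for immune events. The fault is that the ECI term does not match its own definition.

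**The case against.** **Much late toxicity is captured.** SAEs run to 90 days and related SAEs have no time limit. The criterion of another important medical event is broad, and Table 8 describes Grade 3 partly by an indication for hospitalization, so many higher-grade events would qualify. Section 8.1.6.5 follows open events above Grade 1. This stands, and it confines the gap to new-onset, non-serious events.

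**The text is not wholly closed.** The list is introduced with the word include; Section 8.1.2.2 also says AEs are recorded during follow-up; Section 8.1.6.3 lists toxicity assessments among unplanned-visit data. These soften the point without removing it. An open list gives a site no criterion for what else qualifies, the follow-up sentence in 8.1.2.2 conflicts with the 30-day sentence in the same section, and 8.1.6.3 sets no window. Sites could reasonably collect differently.

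**A stronger reading on steroids.** A reader might infer that the steroid exception contradicts Table 3, because a steroid-treated subject would be removed while Table 3 allows restart at Grade 0–1. That follows only if the ECI term is held to the two listed items and the rest of the bullet is ignored. Read as a whole, the documents do not support it.

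**Separate conflicts nearby.** Section 5.2.4 limits toxicity holds to 2 weeks, Section 5.2.5 to 63 days, and Table 3 works to 12 weeks. Section 5.4.1 asks for tapers of at least 4 weeks, while BCG may be delayed for at most 2 weeks with steroids expected to be stopped. These bear more directly on whether a treated subject continues. They also need reconciling, and extending the ECI list would not resolve them.

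**Conclusion.** The point holds in a narrow form. New-onset, non-serious immune-mediated events starting on days 31–90, other than the liver pattern, and the medication given for them, are outside clearly required collection. The cause is the 30-day AE window, which the ECI list does not extend for these events. This assumes that the three 30-day statements govern over the follow-up sentence in Section 8.1.2.2.

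The size of the loss cannot be derived from the documents. A reader might divide the 60 days by the 195 elapsed days from first dose to the end of the ECI window and infer that about 31% of such events are lost. That requires onset to be uniform over the whole period, and the documents give no onset distribution. What can be said is that each missed subject shifts an AE proportion by 6.7 percentage points.

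The steroid wording is a mismatched term that conflicts with Table 3 only on a literal reading. It is worth correcting, but it is secondary to the collection gap.

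**What to change.** 1. In Section 9.1.3.2, add the immune-mediated events named in Table 3 as ECIs, at the grades Table 3 already lists for holding or stopping MK-3475. Table 3 gives no such grade for hypothyroidism, so the sponsor should state a reporting grade. Existing text then carries these events, and their medication under Section 5.3.1, to 90 days.
2. Have the 3-month contact or chart review ask about immune events with onset since the safety visit, recording the onset date.
3. Align the two sentences in Section 8.1.2.2 with each other and with Sections 7.1 and 9.0.
4. In Section 10.1, state that these ECIs enter the AE tabulation, and over what window.
5. Reconcile the ECI term and the removal sentence in Section 5.3.2 with Table 3 and Section 5.4.1 in the same amendment. Because 5.3.2 borrows the ECI term, step 1 also changes what its exception literally covers. Which rule governs is for the sponsor's clinicians.

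The cost is protocol wording and a few more expedited reports among 15 subjects. Section 9.1.3.2 currently gives two reporting times to the manufacturer, 2 working days and 24 hours, and these should be settled at the same time. No new visits are needed, since footnote d of the flow chart already allows chart review and telephone contact. Two limits remain. Capture will be partly retrospective, because no scheduled visit falls on days 31–90. Subjects who start new anticancer therapy within 30 days gain nothing, because their ECI window closes at day 30.

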9.1.3.3 Protocol-Specific Exceptions to Serious Adverse Event Reporting

Efficacy endpoints as outlined in this section will not be reported to Merck as described in Section 9.1.3- Immediate Reporting of Adverse Events to the Sponsor and to Merck, unless there is evidence suggesting a causal relationship between the drug and the event. Any such event will be submitted to the Sponsor within 24 hours and to Merck Global Safety within 2 working days either by electronic or paper media.

Specifically, the suspected/actual events covered in this exception include any event that is disease progression of the cancer under study.

The Sponsor will monitor unblinded aggregated efficacy endpoint events and safety data to ensure the safety of the subjects in the trial. Any suspected endpoint which upon review is not progression of the cancer under study will be forwarded to Merck Global Safety as a SAE within 2 working days of determination that the event is not progression of the cancer under study

Hospitalization related to convenience (e.g., transportation issues etc.) will not be considered a SAE.

Product: MK-3475

Protocol/Amendment No.: Amendment 5, 21 October 2019

9.1.4 Evaluating Adverse Events

An Investigator who is a qualified physician will evaluate all adverse events according to the NCI Common Terminology for Adverse Events (CTCAE), version 4.0. Any adverse event which changes CTCAE grade over the course of a given episode will have each change of grade recorded on the adverse event case report forms/worksheets.

All adverse events regardless of CTCAE grade must also be evaluated for seriousness.

Remainder of Page Intentionally Left Blank

Table 8: Evaluating Adverse Events

An Investigator who is a qualified physician will evaluate all adverse events as to:

V4.0 CTCAE Grading	Grade 1	Mild; asymptomatic or mild symptoms; clinical or diagnostic observations only; intervention not indicated.
	Grade 2	Moderate; minimal, local or noninvasive intervention indicated; limiting age-appropriate instrumental ADL.
	Grade 3	Severe or medically significant but not immediately life-threatening; hospitalization or prolongation or hospitalization indicated; disabling; limiting self-care ADL.
	Grade 4	Life threatening consequences; urgent intervention indicated.
	Grade 5	Death related to AE
Seriousness	A serious adverse event is any adverse event occurring while the subject is enrolled into the study:	
	† Results in death ; or	
	† Is life threatening ; or places the subject, in the view of the investigator, at immediate risk of death from the event as it occurred (Note: This does not include an adverse event that, had it occurred in a more severe form, might have caused death.); or	
	† Results in a persistent or significant disability/incapacity (substantial disruption of one’s ability to conduct normal life functions); or	
	† Results in or prolongs an existing inpatient hospitalization (hospitalization is defined as an inpatient admission, regardless of length of stay, even if the hospitalization is a precautionary measure for continued observation. (Note: Hospitalization for an elective procedure to treat a pre-existing condition that has not worsened is not a serious adverse event. A pre-existing condition is a clinical condition that is diagnosed prior to the use of a Merck product and is documented in the patient’s medical history.); or	
	† Is a congenital anomaly/birth defect (in offspring of subject taking the product regardless of time to diagnosis); or	
	Is a new cancer ; (that is not a condition of the study) or (although not serious per ICH definition, is reportable to the Sponsor within 24 hours and to Merck within 2 working days to meet certain local requirements); or	
	Is an overdose (whether accidental or intentional). Any adverse event associated with an overdose is considered a serious adverse event, for collection purposes. An overdose that is not associated with an adverse event is considered a non-serious event of clinical interest and must be reported within 24 hours to the Sponsor and to Merck within 2 working days.	
	Other important medical events that may not result in death, not be life threatening, or not require hospitalization may be considered a serious adverse event when, based upon appropriate medical judgment, the event may jeopardize the subject and may require medical or surgical intervention to prevent one of the outcomes listed previously (designated above by a †).	
Duration	Record the start and stop dates of the adverse event. If less than 1 day, indicate the appropriate length of time and units	
Action taken	Did the adverse event cause Merck product to be discontinued?	
Relationship Merck Product	Did the product cause the adverse event? The determination of the likelihood that Merck product caused the adverse event will be provided by an Investigator who is a qualified physician. The investigator’s signed/dated initials on the source document or worksheet that supports the causality noted on the AE form, ensures that a medically qualified assessment of causality was done. This initialed document must be retained for the required regulatory time frame. The criteria below are intended as reference guidelines to assist the Investigator in assessing the likelihood of a relationship between the test drug and the adverse event based upon the available information. The following components are to be used to assess the relationship between Merck product and the AE ; the greater the correlation with the components and their respective elements (in number and/or intensity), the more likely Merck product caused the adverse event (AE):	
	Exposure	Is there evidence that the subject was actually exposed to the product such as: reliable history, acceptable compliance assessment (pill count, diary, etc.), expected pharmacologic effect, or measurement of drug/metabolite in bodily specimen?
	Time Course	Did the AE follow in a reasonable temporal sequence from administration of Merck product? Is the time of onset of the AE compatible with a drug-induced effect (applies to trials with investigational medicinal product)?

	Likely Cause	Is the AE not reasonably explained by another etiology such as underlying disease, other drug(s)/vaccine(s), or other host or environmental factors
--	---------------------	---

Relationship to Merck Product (continued)	The following components are to be used to assess the relationship between the test drug and the AE: (continued)	
	Dechallenge	Was Merck product discontinued or dose/exposure/frequency reduced? If yes, did the AE resolve or improve? If yes, this is a positive dechallenge. If no, this is a negative dechallenge. (Note: This criterion is not applicable if: (1) the AE resulted in death or permanent disability; (2) the AE resolved/improved despite continuation of the Sponsor's product; or (3) the trial is a single-dose drug trial; or (4) Sponsor's product(s) is/are only used one time.)
	Rechallenge	Was the subject re-exposed to the product in this study? If yes, did the AE recur or worsen? If yes, this is a positive rechallenge. If no, this is a negative rechallenge. (Note: This criterion is not applicable if: (1) the initial AE resulted in death or permanent disability, or (2) the trial is a single-dose drug trial); or (3) Sponsor's product(s) is/are used only one time). NOTE: IF A RECHALLENGE IS PLANNED FOR AN ADVERSE EVENT WHICH WAS SERIOUS AND WHICH MAY HAVE BEEN CAUSED BY THE PRODUCT, OR IF REEXPOSURE TO MERCK PRODUCT POSES ADDITIONAL POTENTIAL SIGNIFICANT RISK TO THE SUBJECT, THEN THE RECHALLENGE MUST BE APPROVED IN ADVANCE BY THE SPONSOR AS PER DOSE MODIFICATION GUIDELINES IN THE PROTOCOL.
	Consistency with Trial Treatment Profile	Is the clinical/pathological presentation of the AE consistent with previous knowledge regarding Merck product or drug class pharmacology or toxicology?
The assessment of relationship will be reported on the case report forms /worksheets by an Investigator who is a qualified physician according to his/her best clinical judgment, including consideration of the above elements.		
Record one of the following		Use the following scale of criteria as guidance (not all criteria must be present to be indicative of a product relationship).
Yes, there is a reasonable possibility of product relationship.		There is evidence of exposure to Merck product. The temporal sequence of the AE onset relative to the administration of Merck product is reasonable. The AE is more likely explained by Merck product than by another cause.
No, there is not a reasonable possibility of Merck product relationship		Subject did not receive the product OR temporal sequence of the AE onset relative to administration of Merck product is not reasonable OR the AE is more likely explained by another cause than the Merck product. (Also entered for a subject with overdose without an associated AE.)

Product: MK-3475

Protocol/Amendment No.: Amendment 5, 21 October 2019

